Bioven should be administered intravenously dropwise at the initial rate of 0.5-1.0 ml/kg of body weight/hour for 30 minutes. If no adverse reactions occur, the rate of administration may be gradually increased (it is recommended to increase by 0.5-1.5 ml/kg of body weight/hour every 10 min). According to the data from clinical studies the maximum rate of administration is 8.5 ml/kg of body weight/hour.

The study drug is administered only in hospital environment while observing the rules of aseptic. The solution should be of room temperature before use. Cloudy solutions and those containing sediment are not used. For the administration of the drug, it is necessary to use a separate infusion system.

When administering the drug, it is necessary to consider the information specified in the relevant sections of the instructions for medical use: administration details, special safety measures, contraindications, interaction with other medicinal products, etc.

Patients participating in this study may receive concomitant therapy, which is used for the treatment of comorbidities and life-threatening conditions.

It is allowed to use glucocorticoids in a stable dose for at least 2 weeks before starting treatment with the test drug. The need to increase the dose of corticosteroids during the study is considered as ineffective use of the study drug.

Duration of treatment:

The duration of treatment with the study drug for each patient is no less 2 days. The total period of stay in the study is 4 weeks.

Efficacy and safety endpoints: Efficacy:

Primary efficacy endpoint:

| Bioven | |
|----------------------------|--|
| Trial Code: 2021-BV-ITP-BP | |

Page 11 Version 1.4 from July 03, 2023,

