After the informed consent form is signed, the screening tests are performed and the compliance with the inclusion / non-inclusion criteria is evaluated. The patient who passed the screening tests is enrolled in the study.¹

Clinical phase

Patients enrolled in the study receive Bioven at a dose of:

0.8-1.0 g / kg intravenously once a day for 2 consecutive days, the course dose is 1.6-2.0 g / kg. Allowed repeat course at same dosage in period 14-28 days from first infusion, if required.

The CRF records the time of administration of the study drug, the occurrence of possible adverse events.

Prescribed therapy and diagnostic results are recorded in the CRF based on the primary documentation.

Data are entered into the CRF according to the patient management plan.

Follow-up phase and completion of the study

This stage lasts for 4 weeks after the last administration of the drug (possible repeat course is not considered).

In all patients, the platelet count will be determined 48 hours after the start of the first administration of the study drug, on the 7th (\pm 1 day), 14th (\pm 2 days), 21st (\pm 3 days), 28th (+ 1-3 days) days after the start of therapy.

The results of the study are evaluated by endpoints.

Phase-by-phase breakdown and breakdown of visits are detailed in Section 6.4 "Tabulated schedule of events". Information is entered into the CRF after each visit, according to the "Schedule of study events".

The decision on any examinations and diagnostic procedures in routine clinical practice is made and controlled by professionals.

Blood sampling for platelet count is performed 6 times:

- at the screening phase;
- 48 (\pm 3) hours after the start of study drug administration;
- on the 7th (± 1) day from the start of study drug administration;
- on the 14th (± 2) day from the start of study drug administration;
- on the 21st (± 3) day from the start of study drug administration;
- on the 28th (+ 1-3) day from the start of study drug administration.

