First line treatment options include corticosteroids, intravenous immunoglobulin (IV Ig) and intravenous anti-D immunoglobulin (the latter only for non-splenectomised Rhesus-D positive patients). Patients who fail to respond or who relapse face the options of treatment with second line drug therapy or splenectomy but there is no clear evidence to support the best approach. Splenectomy can provide long term efficacy in around 60% of cases. Second line drug therapies include high dose corticosteroids, high dose IV Ig or anti-D Ig, vinca alkaloids and danazol, the immunosuppressants cyclophosphamide, azathioprine and cyclosporine or mycophenolate mofetil, and the anti-CD-20 monoclonal antibody [4].

IVIg have been used in the treatment of ITP since 1981, after the publication of P. Imbach et al., Which proved the high effectiveness of IV Ig in the treatment of ITP in children. [5].

The therapeutic effects of IV Ig in ITP include:

- blockade of neonatal Fc receptors on the surface of endothelial cells and acceleration of catabolism of the whole pool of plasma immunoglobulins, including antiplatelet antibodies;
- inhibition of FcγRIIIa- receptors and phagocytosis mediated by them;
- suppression of the expansion of autoreactive lymphocytes by signal transduction through FcγRIIIa;
- idiotype-mediated inhibition of B-cell receptors and neutralization of cytokinessurvival factors: B-cell activation factor (BAFF) and proliferation-promoting ligand (APRIL) [6,7,8]. The binding of anti-idiotypic antibodies (BP) to membrane-bound Ig G or Ig M B-lymphocytes can transmit inhibitory signals and reduce the production of pathogenic auto-BP [9];
- utilization of active components of complement [10].

In addition, IV Ig drugs cause immune tolerance by modulating subpopulations of Tlymphocytes, namely T-reg- increasing their number and changing the quality of the composition [11].

It is likely that the effect of Ig G therapy in time exceeds the half-life of IV Ig [12].

Immunoglobulin drugs for intravenous administration are not generic drugs and cannot not be interchangeable [15,16].

Clinical studies on the efficacy of intravenous immunoglobulin Bioven 10% solution for infusion in immune thrombocytopenia have not been performed.

2.2 Name and description of the investigational drug.

Composition:

active substance: Human normal immunoglobulin for intravenous administration;

1 ml of the drug contains 0.1 g of normal human immunoglobulin;

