The duration of lymphopenia was also significantly reduced. The median time to achieve the level of lymphocytes 1000 cells/mm3 and above in the study group was 4 days (interquartile range - 3.00-5.00 days), in the control group - 7 days (interquartile range - 3.00-7.50 days), p = 0.0097. Pharmacokinetics properties.

The high level of efficacy of the Bioven product is provided by a fast and 100% entrance of antibodies into bloodstream as well as by normal elimination half-life.

After intravenous administration the bioavailability of the normal human immunoglobulin in the circulating blood is immediate and complete. It is rapidly distributed between the plasma and extravascular liquid, and the balance between intra- and extravascular compartments is reached in approximately 3-5 days.

For normal human immunoglobulin the half-life is approximately 40 days. This half-life period can differ from patient to patient, especially in case of primary immunodeficiency. IgG and IgG-complexes degrade in reticuloendothelial system cells.

A clinical study of individual pharmacokinetic parameters of Bioven was performed and involved 22 patients. Cmax was 19.94 ± 4.73 g/l, Tmax -0.63 hours, AUC(0-t) -8309.60 ± 2631.49 g/year /l. The content of immunoglobulin in blood plasma was consistently kept above the minimum target level of 5 g/l for at least 28 days after a single administration of Bioven.

Clinical particulars.

Therapeutic indications.

The product should be used for adults, children and adolescents for replacement immunotherapy in the treatment of primary and secondary immunodeficiency and related diseases:

- primary immunodeficiency syndromes: congenital agammaglobulinemia, hypogammaglobulinemia, severe combined immunodeficiency, unclassified variable immunodeficiency, Wiskott — Aldrich syndrome;- secondary antibody deficiency syndrome: cytopenia of different genesis (acute and chronic leukemia, aplastic anemia, situation after cytostatic therapy), severe bacterial and toxic and viral infections (including surgical complications accompanying by bacteremia and septicopyemic conditions and for preparation of surgical patients for operation);

| Bioven | Page 24 |
|----------------------------|---------------------------------|
| Trial Code: 2021-BV-ITP-BP | Version 1.4 from July 03, 2023, |

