3. PURPOSE AND OBJECTIVES OF RESEARCH

Objective: To evaluate the efficacy, safety and tolerability of Bioven in patients with chronic primary immune thrombocytopenia, with evidence of non-inferiority compared to the literature data regarding the level of effectiveness of existing IVIG products.

Tasks of study:

- To evaluate the proportion (%) of patients who achieved the response (R) during the study, platelet count> 30x10⁹ / 1 and at least double their initial number, as confirmed by at least 2 blood tests performed every 7 days; absence of bleeding) during therapy with the studied drug Bioven.
- To evaluate the effeciency of the studied drug Bioven in comparison with the literature data
- To evaluate the presence and severity of hemorrhagic syndrome as a result, which is included within 4 weeks after starting therapy;
- To evaluate the proportion (%) of patients who achieved a complete response (CR) during the study (platelet count> 100 x 10^9 / l, confirmed by at least 2 blood tests performed every 7 days; no bleeding) during treatment with the study drug Bioven.
- To evaluate the proportion (%) of patients who did not respond (NR) during the study with a platelet count $<30 \times 10^9$ / L or less than a 2-fold increase in platelet count from baseline. This must be confirmed by at least 2 blood tests with a difference of one day, or the presence of bleeding during therapy with the study drug Bioven.
- To evaluate the proportion (%) of patients who lost the response (R) during the study (a decrease in platelet count (<30 x 10^9 / L, or less than twice the initial or bleeding. Platelet counts should be confirmed at least twice with an interval of 1 day).
- To evaluate the proportion (%) of patients who lost a complete response (CR) during the study, a decrease in platelet count, $<100 \times 10^9$ / l, or the occurrence of bleeding. Platelet counts should be confirmed at least twice with an interval of 1 day).
- To determine the time from the start of treatment with the study drug Bioven to the onset of the response (R);
- To determine the time from the start of treatment with the studied drug Bioven to the onset of a complete response (CR);
- To set the duration of the response (R);
- To set the duration of the complete response (CR);
- To evaluate the frequency and severity of possible adverse events/adverse reactions (AE/AR).

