6th visit (Day +30 \pm 3 days) - physical examination, assessment of the status of the hemorrhagic syndrome, blood sampling to determine platelet counting by the Fonio method, biochemical blood test, Coombs test, determination of Ig G levels (g / l). This is a face-to-face visit. Completion of the study.

Patients' serum samples should be stored frozen at the temperature of -65 - -85 $^{\circ}$ C (second aliquot) to ensure the possibility of performing repeat laboratory tests, if necessary, in the future.

Patients receive Biven 10% solution for infusion, produced by LLC "Biopharma Plasma" at a dose of 0.8-1.0 g / kg 1 time per day for 2 consecutive days, the course dose of 1.6-2.0 g / kg. Allowed repeat course at same dosage in period 14-28 days from first infusion, if required.

Bioven should be administered intravenously dropwise at the initial rate of 0.5-1.0 ml/kg of body weight/hour for 30 minutes. If no adverse reactions occur, the rate of administration may be gradually increased (it is recommended to increase by 0.5-1.5 ml/kg of body weight/hour every 10

| Bioven | Page 43 |
|----------------------------|---------------------------------|
| Trial Code: 2021-BV-ITP-BP | Version 1.4 from July 03, 2023, |

min). According to the data from clinical studies the maximum rate of administration is 8.5 ml/kg of body weight/hour.

The study drug is administered only in hospital environment while observing the rules of aseptics. The solution should be of room temperature before use. Cloudy solutions and those containing sediment are not used. For the administration of the drug, it is necessary to use a separate infusion system.

When administering the drug, it is necessary to consider the information specified in the relevant sections of the instructions for medical use: administration details, special safety measures, contraindications, interaction with other medicinal products, etc. Including, but not limited to, measures to control the condition of the coagulation system, hydration levels, renal function, etc.

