The variable is analyzed for patients who achieved a response (R) during the study.

Non-response (NR) during the study.

NR is determined according to the criteria *:

- Patients with NR: $patient count < 30 \times 10^{9}$ /L or less than two-fold increase of baseline platelet count. This must be confirmed by at least 2 blood tests performed approximately 1 day apart, or the presence of bleeding;

The categories of the variable will be defined as "Yes" or "No" respectively.

The variable is analyzed relative to the total number of patients included in the analysis.

Loss of response (loss of R).

R loss is determined according to the criteria *:

 Patients with loss R: a decrease platelet count < 30 x 10⁹/L or less than two-fold increase of baseline platelet count, or the occurrence of bleeding. Platelet counts confirmed at least 2 blood tests performed approximately 1 day apart.

The categories of the variable will be defined as "Yes" or "No" respectively.

The variable is analyzed for patients who achieved a response (R) during the study.

Loss of complete response (loss of CR).

CR loss is determined according to the criteria *:

Patients with loss of CR: decrease platelet count $< 100 \times 10^9$ /L, or the occurrence of bleeding. Platelet counts confirmed at least 2 blood tests performed approximately 1 day apart.

The categories of the variable will be defined as "Yes" or "No" respectively. The variable is analyzed for patients who achieved a complete response (CR) during the study.

Time (in days) from treatment start to onset of a response (R);

A Kaplan Meier curve will be constructed and the median time to event will be estimated. The variable is analyzed for patients who achieved a response (R) during the study.

Time (in days) from treatment start to onset of a complete response (CR);

A Kaplan Meier curve will be constructed and the median time to event will be estimated. The variable is analyzed for patients who achieved a complete response (CR) during the study.

Duration (in days) of response (R);

A Kaplan Meier curve will be constructed and the median time to event will be estimated. The variable is analyzed for patients who achieved a response (R) during the study.

Duration (in days) of complete response (CR);

A Kaplan Meier curve will be constructed and the median time to event will be estimated. The variable is analyzed for patients who achieved a complete response (CR) during the study.

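### The Kaplan-Meier median is the only figure planned for duration of R and CR, yet observation ends at about Day 28 to 33, so it may well not be reached, and no fallback or censoring rule is stated

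*Combined protocol and SAP*

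**What the plan says.** Section 3 makes the duration of R and of CR study objectives, and Section 8.2 lists both, in days, as secondary endpoints. Section 10.3.3 handles each in the same way: "A Kaplan Meier curve will be constructed and the median time to event will be estimated". The set is restricted: "The variable is analyzed for patients who achieved a response (R) during the study" (for CR, those who achieved CR). Loss of R and loss of CR are yes/no variables over the same responders.

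On follow-up, the Synopsis states: "The total period of stay in the study is 4 weeks". It places the last platelet count "on the 28th (+ 1-3) day from the start of study drug administration", so up to Day 31. Section 6.2 gives the last visit as Day 30 ± 3, so up to Day 33. The Synopsis adds that a possible repeat course, allowed 14 to 28 days after the first infusion, does not extend follow-up.

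On persistence there are two background statements. Section 2.1 says: "It is likely that the effect of Ig G therapy in time exceeds the half-life of IV Ig". Section 2.2, under pharmacokinetics, says: "For normal human immunoglobulin the half-life is approximately 40 days".

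Section 10.3.3 refers to censored data and names Kaplan-Meier, but states no censoring date for patients still in response and no summary for a median that is not reached. Section 10.3.6 fills missing data by last observation carried forward (LOCF).

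**The concern.** A Kaplan-Meier median exists only if the curve falls to 50% within observation. If response commonly outlasts four weeks, the one number planned for the duration objective will be missing, or will be read from the end of the curve where few patients remain at risk. With no alternative specified, the replacement would be chosen after the data are seen.

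The percentage with loss of response has a related weakness. It divides by all responders, whenever they responded. A patient first in response on Day 21 and confirmed on Day 28 has no scheduled follow-up after confirmation, yet counts fully as not having lost response. A low percentage could then be taken as durable effect when it partly reflects short observation.

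**Working it through.** The plan gives no figure for duration. Its sample size, used here only to set the number of responders, reproduces: (1.96 + 1.28)² × 0.78 × 0.22 / 0.25² = 28.8, so 29; 29 / 0.8 = 36.25 against 36 stated. The Synopsis and Section 4.1 give 40. At the planned 78% response, 29, 36 or 40 patients yield about 23, 28 or 31 responders.

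**Observable duration**
- Onset at 48 hours (Day 2): 28 − 2 = 26 days, 31 − 2 = 29, or 33 − 2 = 31.
- Onset at Day 7: 21, 24 or 26 days.

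**Earliest confirmation.** R needs two counts at least 7 days apart (Section 8.1). The 48-hour count and the Day 7 ± 1 count are only about 6 days apart at most, so they cannot confirm each other. On scheduled visits the first possible confirmation is Visit 4, nominal Day 14. That leaves 14, 17 or 19 days in which a confirmed response can be seen to be lost.

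**Expected loss.** Assume exponential durations with true median M. The share lost within t days is 1 − 2^(−t/M). For M = 40 and t = 26: 1 − 2^(−0.65) = 36%. For t = 29 it is 40%, and for t = 31 it is 42%.

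**Chance that the median is reached**, calculated in two ways:
- Binomial: at least half of 23, 28 or 31 responders lose response by Day 28, all with onset at 48 hours and no confirmation requirement.
- Simulation: 4,000 runs, 36 patients, 78% initial response, onset at 48 hours in 80% and Day 7 in 20% (assumed), response still present at Day 14 required, last count Day 28. M is the median of all initial responses.

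| M (days) | Loss by Day 28 / 31 / 33 | Binomial, Day 28 | Simulation: exponential / Weibull shape 2 |
|---|---|---|---|
| 14 | 72 / 76 / 78% | about 99% or more | 62% / over 99% |
| 21 | 58 / 62 / 64% | 77–84% | 22% / 79% |
| 28 | 47 / 51 / 54% | 39–47% | 5% / 16% |
| 40 | 36 / 40 / 42% | 6–10% | 0.6% / 0.3% |
| 60 | 26 / 28 / 30% | under 1% | 0% / 0% |

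With the last count at Day 31, the binomial chance at M = 40 rises to 12–17%.

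The simulation gives lower chances in the exponential case because early losses never become confirmed R. With exponential durations, a response that began on Day 2 and still holds on Day 14 has median duration 12 + M from onset: 52 days for M = 40, 33 for M = 21 and 26 for M = 14. Against 26 observable days, M = 14 is the break-even (M = 17 if the last count is Day 31).

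**Unequal time at risk in the crude loss percentage.** Take M = 40 and a last count at Day 28. Confirmed at Day 14, 14 days remain: 1 − 2^(−14/40) = 22% observed loss. Confirmed at Day 21, 7 days remain: 1 − 2^(−7/40) = 11%. Confirmed at Day 28: 0%. Durability is the same in all three, so the pooled percentage depends on when patients responded.

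**The case against.** The strongest reply is that the 40-day premise is not a protocol expectation for platelet response. The Section 2.1 sentence is hedged and concerns IgG therapy in general. The half-life in Section 2.2 is pharmacokinetic and is said to vary between patients. The protocol also allows a repeat course on Days 14 to 28 and schedules an extra count after a fall below 30 × 10⁹/L, so it foresees waning within the window. All of this stands, and it makes the conclusion conditional.

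Nor do the figures transfer to CR. A patient can lose CR by falling below 100 × 10⁹/L while still in R, so the CR median could be reached sooner. What applies equally to CR is the short window and the missing fallback.

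A reader might infer that loss of response is understated. The documents do not support that as a general statement. Section 3 defines loss as loss during the study, and short follow-up alone does not bias a properly censored Kaplan-Meier curve. The narrower point stands: no such curve is planned for the loss percentages, which mix unequal times at risk.

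Finally, these are secondary endpoints, and the non-inferiority conclusion does not rest on them. An unreached median could simply be reported as such, and the planned curve already contains the 14-day and 21-day proportions. That limits the consequence, but it does not supply a prespecified number for the objective.

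**Conclusion.** The point holds conditionally. The median duration of R may well not be reached. At a true median of 40 days the chance of reaching it is roughly 0.3% to 17% across the calculations above; at 60 days it is about 1% or less. A reader might infer that the median cannot be estimated at all. The documents do not support this: at true medians of 14 to 21 days, which they do not exclude, the chance runs from about 22% to over 99%, depending on the shape of the distribution and the confirmation requirement.

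These figures rest on assumed distributions and onset times, and on the plan's 78% response rate. The 26 to 31 day limit, the absence of a censoring rule and fallback, and the unequal time at risk behind the loss percentages need none of those assumptions. The matter should be corrected in the endpoint and analysis text; it does not touch the primary conclusion.

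**What to change.** In Sections 8.2 and 10.3.3:

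- Summarise duration by Kaplan-Meier proportions still in R, and in CR, at fixed times after onset (for example 14 and 21 days) with 95% confidence intervals, plus a restricted mean to a stated common horizon. Say which count marks onset.
- Censor patients still in response at their last actual platelet count, and do not apply LOCF to these variables.
- Report a median only if the curve falls to 50%.
- Report loss of R and of CR as Kaplan-Meier estimates, labelled as loss within the 28-day study.
- State how a repeat course is treated in this analysis. Counting it as loss, censoring at it and ignoring it estimate different things.
- State that duration beyond the last visit was not studied.

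The dates of the last visit in the Synopsis and Section 6.2 must be reconciled, because the horizon depends on them.

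The cost is wording and a few extra summaries from data already collected, with no added visits or patients. The downside is a more modest duration claim.

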8 EVALUATION OF EFFICIENCY

8.1 Primary efficacy endpoint:

Part (percent) of patients with response (R).

R is determined according to the following criteria:

- Patients with R: platelets count $> 30x10^{9}/L$ and at least a two-fold increase from the baseline count. This must be confirmed by at least 2 blood tests at least 7 days apart, and the absence of bleeding;

The primary efficacy variable is achievement of R during the study (yes/no).

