For variables that are "time to event" survival curves will be constructed in each group using the Kaplan-Meier method, median survival will be estimated, and group comparisons will be made using the log-rank test. If the survival curves intersect, then Cox regression will be used to compare the groups according to these variables.

| Bioven | Page 69 |
|----------------------------|--------------------------------|
| Trial Code: 2021-BV-ITP-BP | Version 1.4 from July 03, 2023 |

To evaluate the significance in the dynamics in the case of evaluating the parameter on two visits (before and after):

- To assess the dynamics of quantitative variables, the Student's test for paired data or the Wilcoxon signed rank test will be applied, depending on the results of testing the normality of the distribution of differences [after - before] using the Shapiro-Wilk test.

- To assess the dynamics of categorical variables in groups, the McNemar criterion or the criterion of homogeneity of marginal frequencies will be applied, depending on the number of categories.

- To assess the statistical significance of differences in categorical variables in unrelated groups, Pearson's chi-square or Fisher's exact test will be applied (depending on the frequency distribution in table 2*2).

To evaluate the dynamics in the case of measuring variables on more than two visits, methods of univariate analysis of variance (ANOVA) will be used followed by contrast analysis (simple contrasts) or a posteriori analysis using Tukey's test. Analysis of covariance (ANCOVA) will be used to compare those variables for which the data were heterogeneous at baseline.

To verify the prerequisites for the application of variance and covariance analyses, a check of the normality of the data distribution and their residuals will be performed using the Shapiro-Wilk test. If the residuals are not normally distributed, or if the data fail the normality test, an appropriate rank analysis will be performed.

For the Shapiro-Wilk test, the significance level will be 0.01, and for other criteria - 0.05. In the event of the effect of multiple comparisons, an adjustment of the level of significance will be applied using the Holm method or the Benjamini-Hochberg method.

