10.3.3. Analysis of effectiveness

Additional information about the statistical model for evaluating the effectiveness of the drug by the main variable is given in Section 10.1. "The content of statistical analysis".

A) The primary outcome of efficiency – Proportion (%) of patients with response (R).

Primary efficiency variable – achievement of R during the study. *R is defined according to criteria* *:

| Bioven | Page 71 |
|----------------------------|--------------------------------|
| Trial Code: 2021-BV-ITP-BP | Version 1.4 from July 03, 2023 |

- Patients with R: the number of platelets > $30x10^{9}/l$ and at least a two-fold increase from the baseline count. This must be confirmed by at least 2 blood tests performed once every 7 days and the absence of bleeding;

The categories of the variable will be defined as "Yes" or "No" respectively.

* The criteria are defined according to the Guideline on the clinical investigation of human normal immunoglobulin for intravenous administration (IVIg), EMA/CHMP/BPWP/94033/2007 rev. 4, 16 December 2021 as well as according to the criteria of the international working group on ITP in 2009. (Rodeghiero, F., Stasi, R., Gernsheimer, T., Michel, M., Provan, D., Arnold, D. M., ... & George, J. N. (2009). Standardization of terminology, definitions, and outcome criteria in immune thrombocytopenic purpura of adults and children: report from an international working group. Blood, The Journal of the American Society of Hematology, 113(11), 2386-2393.);

B) Secondary effectiveness variables.

For variables assessed once at the final visit, descriptive statistics methods will be used to describe these variables (for quantitative parameters - n, arithmetic mean, median, standard deviation, minimum and maximum value; for categorical parameters - number and share in %). 95% confidence intervals will be calculated. In the case of measuring variables at more than two visits, one-way analysis of variance (ANOVA) methods will be used.

Censored data will be analyzed using the Kaplan-Meier method or the log-rank test.

Secondary efficacy endpoints are transformed into corresponding efficacy variables:

Achieving a complete response (CR) during the study.

CR is determined according to the criteria *:

 Patients with CR: platelets count > 100 x 10⁹/L, which is confirmed by 2 blood tests performed at least 7 days apart and the absence of bleeding;

The categories of the variable will be defined as "Yes" or "No" respectively.

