10.4. Data set for analysis

ITT (Intention-to-treat population) - all study participants who took the study drug at least once. Data from this sample will be used for safety analysis.

PP (Per Protocol) - all patients who met the requirements of the protocol. This population includes all patients who received protocol therapy in full, completed all scheduled visits, and had no significant protocol deviations. The data obtained on this sample will be used for analysis according to the criteria of drug effectiveness.

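### Time to R and time to CR are estimated by Kaplan-Meier in achievers only, so each median is conditional on a later outcome, can only equal or precede the all-patient median, and is finite however few respond

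*Combined protocol and SAP*

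**What the plan says.** Section 8.2 lists time from treatment start to onset of R, and to onset of CR, as secondary endpoints. Section 3 lists the same two times as study tasks. Neither place limits them to responders.

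The limit appears in section 10.3.3 B. For time to R, a Kaplan-Meier curve is built and the "median time to event will be estimated. The variable is analyzed for patients who achieved a response (R) during the study". For time to CR: "The variable is analyzed for patients who achieved a complete response (CR) during the study". These sentences recur under other endpoints, including the durations of R and CR. The point here concerns only the two times to onset.

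No general rule brings the other patients back. Section 10.1 says "survival curves will be constructed in each group using the Kaplan-Meier method, median survival will be estimated", and 10.3.3 B opens with "Censored data will be analyzed using the Kaplan-Meier method or the log-rank test". Neither says how a patient who never responds enters the curve. For non-response (NR), the same section does use the full denominator: "The variable is analyzed relative to the total number of patients included in the analysis".

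R itself is settled only after treatment start. Section 8.1 requires: "This must be confirmed by at least 2 blood tests at least 7 days apart, and the absence of bleeding". The efficacy set is per protocol (PP). Section 10.4 says of it: "The data obtained on this sample will be used for analysis according to the criteria of drug effectiveness".

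**The concern.** The clock starts at the first infusion, but entry to the curve depends on something learned at least a week after onset. A curve made up only of patients who had the event must fall to zero. Kaplan-Meier then has no censoring to handle and reduces to the empirical distribution of onset among responders.

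The resulting median answers this question: given that a patient responds, how soon? The endpoint as worded in sections 3 and 8.2 reads as a different question: how soon do treated patients respond? The two answers separate as the response rate falls. The achiever-only figure does not worsen when fewer patients respond, and a handful of responders still gives a finite number of days. With a single arm, no concurrent group would show this.

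**Working it through.** **Inputs from the plan.** Planned response rate 78%, cited literature range 60–80%, and minimum evaluable sample 29 (section 10.2). Platelet counts at 48 hours and about Days 7, 14, 21 and 28 (Synopsis). The plan gives no onset distribution, no CR rate and no expected median.

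**Anchor.** The plan's sample size reproduces: (1.96 + 1.28)² × 0.78 × 0.22 / 0.25² = 28.82, rounded up to 29.

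**Who is in the curve.** At 78%, 29 × 0.78 = 22.6, so about 23 patients enter time to R. All 23 have the event, none is censored, and about 6 are left out. At 60%, 29 × 0.60 = 17.4, so about 12 are left out.

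**General result.** Let π be the response rate and F(t) the cumulative onset among responders. With every patient kept and non-responders followed to Day 28 without the event, the curve is 1 − πF(t). It reaches one half where F(t) = 0.5/π. The achiever-only median is where F(t) = 0.5. Since 0.5/π ≥ 0.5, the all-patient median can never be earlier.

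| π | Quantile of responder onset giving the all-patient median |
|---|---|
| 80% | 0.5/0.80 = 62.5th percentile |
| 78% | 0.5/0.78 = 64.1th percentile |
| 60% | 0.5/0.60 = 83.3th percentile |
| below 50% | not reached |

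**In days, under assumed onset patterns.** Onset is dated at the first qualifying count.

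- 35/45/15/5% of responders at Days 2/7/14/21: cumulative 35/80/95/100%, achiever-only median Day 7.
  - π = 78%: all-patient cumulative 27/62/74/78%, median Day 7. No difference.
  - π = 60%: 21/48/57/60%, median Day 14.
  - π = 40%: 14/32/38/40%, not reached.
- 55/30/10/5%: cumulative 55/85/95/100%, achiever-only median Day 2.
  - π = 78%: 43/66/74/78%, median Day 7.

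**Sampling variation.** The check used 2,000 simulated trials of 29 patients for each combination of rate and pattern. The four assumed patterns were 70/22/5/3, 50/35/10/5, 55/30/10/5 and 30/45/15/10%.

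- The all-patient median was never the shorter one.
- It was longer in 20–52% of trials at 78%, in 73–85% at 60%, and in about 99% at 40%.
- At 40% it was not reached in 85–88% of trials.

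**CR.** Entry requires a count below 30 × 10⁹/L and CR a count above 100 × 10⁹/L, so, taking the entry count as baseline, a patient with CR also meets the count criterion for R. An all-patient median time to CR therefore exists only if (R rate) × (CR rate among responders) is at least 0.5. At a 78% R rate, at least 0.5/0.78 = 64% of responders must reach CR. At 60%, at least 83% must.

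**How non-responders are handled.** Take the first pattern with π = 60%, per 100 patients. Carrying all 40 non-responders forward gives 0.79 at Day 2 and 0.52 at Day 7, so the median is Day 14. Now censor c of the 40 at Day 2. The Day 7 value becomes 0.79 × (1 − 27/(79 − c)), which is at or below 0.5 once c ≥ 6 (at c = 6: 0.79 × 46/73 = 0.498). Censoring six known failures early would bring the median back to Day 7.

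**The case against.** The restriction is not hidden. Section 10.3.3 B states the analysis set under each endpoint, and time to onset among responders is a legitimate description. The plan also reports the proportion with R, and NR over all analysed patients, so a reader could rebuild 1 − πF(t) for R. This stands, and it reduces the fault to a missing label and an estimator with nothing to estimate. It is weaker for CR: section 10.3.3 B analyses the CR proportion among R achievers, so two proportions must be combined first.

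A reader might infer that the planned medians are simply too short. The documents do not support that as a flat statement. Under the first assumed pattern the two medians agree whenever the response rate is at least 0.5/0.80 = 62.5%, which covers most of the cited 60–80% range. 'Shorter or equal' is what can be shown.

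A reader might also infer that the choice tilts the trial's conclusion towards the drug. It does not. These endpoints have no comparator, threshold or planned test that decides anything, and section 10.3.7 draws non-inferiority from the main variable alone.

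Finally, adding all non-responders and censoring each at the last platelet count would be a poor remedy. The Synopsis and section 4.3 count a corticosteroid increase as ineffectiveness of the study drug. Censoring such patients early treats them as still able to respond, which can itself shorten the median. That objection stands and shapes the fix.

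**Conclusion.** The point holds as a problem of estimand and labelling in two secondary endpoints. As written, both medians are conditional on achieving the event. They can equal or precede the all-patient medians but never follow them, and they exist at any response rate above zero. The shift is from the responders' 50th percentile to their 64th at 78% and their 83rd at 60%. Below 50% the all-patient median is not reached. These quantiles need no onset assumption, only that non-responders are carried to Day 28.

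Every figure in days rests on assumed onset patterns, and the 40% rate, read as a possible CR rate, is also assumed. At the planned 78% the difference may be nil on this visit grid. The responder restriction is appropriate for duration of R and CR, where the clock starts at response and a patient still in response can be censored. The primary R proportion and the non-inferiority conclusion are unaffected.

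**What to change.** Amend section 10.3.3 B as follows.

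- Include every patient in the efficacy analysis set in the time-to-R and time-to-CR curves, by Kaplan-Meier or cumulative incidence.
- Carry patients without the event as non-events to Day 28, including those the plan already counts as treatment failures. Censor at the last platelet count only patients lost to follow-up for reasons unrelated to efficacy.
- Report 'not reached' where the curve does not cross one half.
- Keep the achiever-only median and range as a descriptive line labelled 'among responders'.
- Leave duration of R and duration of CR restricted to achievers.

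Name the set explicitly. Section 10.4 makes it PP, with all visits completed, while section 5.3 keeps patients who drop out during follow-up in the efficacy analysis. Under PP the new curves would describe PP patients, not everyone treated.

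The cost is a change of wording, with no new visits, data or patients. The downside is that the reported median may be later or 'not reached'.
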